 - b. Significant anemia – known recent hemoglobin <9.5 gm/dL

PROTOCOL TITLE: A Randomized Trial of Mifepristone Antagonization with High-Dose Progesterone to Prevent Medical Abortion

- c. Clinically significant cardiovascular disease (angina, valvular disease, arrhythmia, or congestive heart failure)
- d. Breastfeeding
- e. Coagulopathy or therapeutic coagulation
- f. Ultrasound evidence of molar or ectopic pregnancy
- g. Chronic systemic corticosteroid use
- h. Adrenal disease
- i. Sickle cell anemia with frequent/recent crises
- j. Glaucoma

- 2. IUD in place during conception, even if removed.
- 3. Peanut allergy.
- 4. Known intolerance of mifepristone or progesterone.
- 5. Any other condition, that in the opinion of the clinician, would contraindicate mifepristone, progesterone or medical abortion.

Pregnant women will be included in this research. This study evaluates effect of high-dose progesterone on initiation of medical abortion and only pregnant women can have an abortion. Potential subjects must have gone through appropriate informed consent for surgical abortion per the standard of care within the UCD Department of Obstetrics and Gynecology prior to consent and screening for this research trial.

5) Study Timelines

Subject participation: approximately 15-17 days

Study timeline

- Duration of enrollment: 11 months (Anticipate Feb 2019 through Dec 2019)
- Completion of primary analysis: 2 months after completion of follow-up (Anticipate Feb 2020)

6) Study Endpoints

Primary endpoint: continuing pregnancy with presence of gestational cardiac activity after two weeks of study treatment

Secondary endpoints:

- Expulsion rates over two weeks following mifepristone treatment
- Pathology changes in trophoblast in a subset of dilation and curettage specimens
- Change in hCG and progesterone levels during treatment
- Tolerability of treatment
 - Ability to continue treatment for two weeks
 - Adverse events (side effects) related to progesterone or placebo after mifepristone including but not limited to nausea, vomiting, headache, mood changes, cramping, vaginal spotting, vaginal bleeding

PROTOCOL TITLE: A Randomized Trial of Mifepristone Antagonization with High-Dose Progesterone to Prevent Medical Abortion

- Safety outcomes: adverse events related to medical safety (e.g., hemorrhage, emergency department visits, emergent dilation and curettage procedures)

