- On days 3 and 4, take the study treatments about 12 hours apart, one dose in the morning and one in the evening.
- On day 5 through the end of the study, take the study treatment in the morning, at about the same time every day.
- Subjects will be provided with:
 - A daily diary to mark down use of the study drug, adverse effects, and bleeding. The diary will also include information on baseline pregnancy symptoms (present when she started the study). Subjects will be instructed to mark down any adverse effects (e.g., nausea, headache, mood changes) on the back of the diary; for any pregnancy symptom present at baseline, the subject will be instructed only to mark down if this symptom becomes worse than baseline.
 - An information sheet with study office phone numbers and instructions related to expected bleeding and cramping should the pregnancy expel after mifepristone treatment.
- Study day 2: the study site will contact the subject by phone around the time that study treatment is supposed to be started.
- Follow-up Visits: schedule on study days 4 (± 1 day) and 8 (± 1 day) at UCD Family Planning Research office.
 - Diary will be reviewed.
 - Study drug container will be reviewed and remaining drug counted by study staff.
 - The subject will be asked if she is tolerating the treatment and willing to continue study participation.
 - Two 5 mL tubes of blood will be obtained for serum hCG and progesterone level.
 - Ultrasonography will be performed to evaluate for presence of the gestational sac, interval growth and presence of gestational cardiac activity; the exam should preferentially be performed vaginally unless the gestational age or subject anatomy requires abdominal sonography for clearer visualization.
 - If gestational cardiac activity is absent, the visit will be considered an exit visit.
 - Collect remaining study drug and diary.
 - Refer subject to the original referral source (PPMM, FPA or the UCD Family Planning clinic) for completion of follow-up care; a patient from PPMM or FPA can request to complete care at UCD.
 - Referrals for PPMM-referred subjects returning to PPMM will be made to the Sacramento B Street Clinic.
 - Referrals for FPA-referred subjects returning to FPA will be made to the Sacramento Clinic.

PROTOCOL TITLE: A Randomized Trial of Mifepristone Antagonization with High-Dose Progesterone to Prevent Medical Abortion

- The subject will be exited from the study after a final outcome is determined by the clinical team.

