- If the pregnancy is expelled, the visit will be considered an exit visit.
 - Collect remaining study drug and diary.
 - Refer subject to the original referral location (PPMM Sacramento B Street Clinic, FPA Sacramento Clinic or the UCD Family Planning clinic) for completion of follow-up care; a patient from PPMM or FPA can request to complete care at UCD.
 - Referrals for PPMM-referred subjects returning to PPMM will be made to the Sacramento B Street Clinic.
 - Referrals for FPA-referred subjects returning to FPA will be made to the Sacramento Clinic.
 - The subject will be exited from the study after a final outcome is determined by the clinical team.
- If the subject is continuing in the study, she will be reminded of the correct timing of study treatment intake, to fill our her diary daily, and to bring her diary and study drug with her to the next visit.
- Study exit visit: schedule for study day 15-17
 - Scheduled exit visits (study day 15-17) should occur through the original referral source (PPMM, FPA or the UCD Family Planning clinic) but a patient from PPMM or FPA can request to complete care at UCD.
 - Visits for PPMM-referred subjects returning to PPMM will occur at the Sacramento B Street Clinic.
 - Visits for FPA-referred subjects returning to FPA will occur at the FPA Sacramento Clinic.
 - Diary will be reviewed and collected from the participant.
 - Study drug container will be collected and remaining drug counted by study staff.
 - Two 5 mL tubes of blood will be obtained for serum hCG and progesterone level.
 - Ultrasonography will be performed to evaluate for presence of the gestational sac, interval growth and presence of gestational cardiac activity; the exam should preferentially be performed vaginally unless the gestational age or subject anatomy requires abdominal sonography for clearer visualization.
 - A surgical abortion will be performed through routine care if pregnancy has not passed and patient desires.
- If a subject desires to exit the study early (have a surgical abortion prior to Day 15-17), the exit visit procedures should be performed on the day of the surgical abortion.

PROTOCOL TITLE: A Randomized Trial of Mifepristone Antagonization with High-Dose Progesterone to Prevent Medical Abortion

- Unscheduled visits: to occur if the subject has any medical concerns or experiences heavy bleeding which may indicate loss of viability or passage of pregnancy
 - Diary will be reviewed.

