The research database will be banked indefinitely for the purpose of future research questions and will contain only de-identified information as above. The database will be maintained on the UCD server in a file with limited access to Family Planning research team. The data can be used for analyses as approved through this IRB submission; other evaluations will require a separate IRB submission to review the de-identified data.

10) Provisions to Monitor the Data to Ensure the Safety of Subjects

- Safety data will be collected throughout the study through diaries of potential medication side effects.
- Adverse event (AE): adverse experience such as symptom, physical exam finding, or worsening of a preexisting condition that has a temporal association with research participation. Causal relationship with study treatment is not necessary to designate an AE.
- Serious adverse event (SAE): adverse event that requires hospitalization, causes significant disability, causes a birth defect, is life threatening or results in death.
- AEs will be logged and reviewed by an investigator for study drug relationship
- Any SAE will be reported to the principal investigator. The participant will be managed medically as indicated. All source data will be reviewed. Physician investigators will assess for causality or relatedness of the adverse experience to the study.
- SAEs will be summarized at annual IRB renewal submission. SAEs that are unanticipated and thought to be related to the study (thereby placing research subjects at higher risk of harm than originally thought) will be reported to the IRB by the principal investigator within five days of becoming aware of the event.
- The study will be reviewed approximately twice monthly at the Family Planning division research meeting, which includes all research staff. Any concerns regarding individual or trends in AEs will prompt further review of the study and consideration of study termination.
- Study allocation will remain concealed except in a scenario in which revealing allocation is clinically important for the participant's management

11) Withdrawal of Subjects

Participants may elect to discontinue the study for any reason. Participants will be withdrawn from the study pending investigator review of AE that warrants removal or any SAE (see Section 10).

12) Risks to Subjects

1. Mifepristone side effects:

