The mifepristone label does not provide side effects for mifepristone alone; side effects are provided for the combination of mifepristone and misoprostol. The data,

PROTOCOL TITLE: A Randomized Trial of Mifepristone Antagonization with High-Dose Progesterone to Prevent Medical Abortion

especially as it relates to bleeding, does not reflect just mifepristone use. Data on mifepristone side effects are taken from reference #19.

Nausea	39%
Cramping	27%
Headache	20%
Dizziness	20%
Warmth/chills	19%
Vomiting	14%
Spotting	9%
Diarrhea	7%

For this study, we expect bleeding and/or spotting to occur in all subjects (even though most will not expel the pregnancy).

2. Progesterone side effects:

From the Prometrium label – use in premenopausal women at 400 mg/day

Dizziness	24%
Abdominal Pain (Cramping)	20%
Headache	16%
Breast Pain	16%
Infection Viral	12%
Musculoskeletal Pain	12%
Fatigue	8%
Abdominal Distention (Bloating)	8%
Diarrhea	8%
Nausea	8%
Back Pain	8%
Irritability	8%
Coughing	8%

3. Teratogenicity: if women decide to continue the pregnancy after receiving one or both study treatments, mifepristone and progesterone are not considered teratogens.

Teratogenicity with standard medical abortion treatment is related to misoprostol, which is not being used in this study.

4. Pregnancy expulsion: few women expel the pregnancy with mifepristone 200 mg treatment in medical abortion studies. However, few studies follow women for up to 2 weeks. We do not know the spontaneous expulsion rate with this treatment but expect the rate may be around 30%; Delgado and colleagues estimate the oral progesterone regimen in this study has an efficacy of 68% (10) meaning that at least ~30% will expel the pregnancy, even with progesterone treatment.

If pregnancy expulsion occurs, the woman will experience bleeding and cramping. The cramping can be very strong for several hours and is typically treated with NSAIDs. Subjects will be made aware that if they need stronger pain medication they can contact the physician on call. Initial bleeding may be similar to, or greater than, a

PROTOCOL TITLE: A Randomized Trial of Mifepristone Antagonization with High-Dose Progesterone to Prevent Medical Abortion

heavy period and may include blood clots and tissue. Within a few hours bleeding is usually equal to or less than a typical menses. After passing the pregnancy, bleeding or spotting can be expected for an average of 9-16 days and may last for up to 30 days.

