Approximately 1-5% of women may experience very heavy bleeding, which is soaking through more than two sanitary pads per hour for two hours in a row.

In 1% of women or less, a suction aspiration (surgical abortion) to stop the bleeding may be indicated. Very rarely (less than 1/1,000 women), the amount of blood loss may be life-threatening and a blood transfusion may be necessary.

In 1-5% of women, incomplete expulsion may occur which would also necessitate a suction aspiration (surgical abortion). In less than 1% of women, a uterine infection could occur from incomplete abortion.

5. Phlebotomy: Temporary discomfort from the needle stick, bleeding at the needle puncture site and bruising may occur. Very rarely (1% or less), fainting may occur.
6. Vaginal ultrasound: Temporary discomfort similar to a pelvic examination may occur.
7. Delay in surgical abortion: A delay of up to 2 weeks in the gestational age range for this study does not incur increased surgical risk.
8. Privacy: There is a risk that protected health information could become known to someone not involved in this study. A unique study number will be assigned and study records will remain in a locked cabinet of a locked research-only office.

13) Potential Benefits to Subjects

There is no direct benefit of study participation for the subject.

14) Multi-Site Research

The UCD study site oversees the study which will also have study procedures performed at PPMM Sacramento B Street Clinic and FPA Sacramento Clinic. Study procedures will only include referral, obtaining specimens (e.g., phlebotomy), and sending copies of medical records to the UCD study site. Thus, no staff at the PPMM Sacramento B Street Clinic or FPA Sacramento Clinic will be considered study personnel. The site physicians and staff coordinators at PPMM Sacramento B Street Clinic and FPA Sacramento Clinic will work administratively with the UCD study physicians and coordinator to ensure the following:

- The site conducts the study appropriately.

PROTOCOL TITLE: A Randomized Trial of Mifepristone Antagonization with High-Dose Progesterone to Prevent Medical Abortion

- The PPMM and FPA co-investigators and site coordinators have the most current version of the protocol.
- Planned Parenthood Federation of America (PPFA) approval is obtained before the PPMM site begins to refer subjects.
- All modifications are communicated to PPMM and FPA.

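### Safety recording by the study stops when a loss or expulsion is found early, so later events may go unrecorded and diary time depends on the efficacy outcome

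*Combined protocol and SAP*

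**What the plan says.** - **Section 7, Follow-up Visits (days 4 and 8, each ± 1 day).** "If gestational cardiac activity is absent, the visit will be considered an exit visit", and likewise "If the pregnancy is expelled, the visit will be considered an exit visit". In both cases staff are told: "Collect remaining study drug and diary". The woman is then referred for completion or follow-up care. The Unscheduled visits block has the same collection and referral steps.
- **What happens afterwards.** Formal exit waits until the clinical team has settled the final outcome, and copies of the referral site's visit records are obtained. No further diary, study call or study visit is specified.
- **The diary.** Section 7 has it record drug use, adverse effects and bleeding. Section 10 says: "Safety data will be collected throughout the study through diaries of potential medication side effects".
- **Expected course.** Section 12, item 4: "After passing the pregnancy, bleeding or spotting can be expected for an average of 9-16 days and may last for up to 30 days".
- **Endpoints.** Section 6 counts spotting, bleeding and cramping under tolerability. Its examples of safety outcomes are hemorrhage, emergency department attendance and emergent curettage.
- **Analysis.** Section 8 compares outcomes, adverse effects among them, by Fisher's exact or chi-square tests. It states no common observation window and no allowance for length of observation.
- **Duration.** Section 5: "Subject participation: approximately 15-17 days".

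**The concern.** Two things are at stake.

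The first is completeness. The diary can be withdrawn while a listed endpoint, bleeding, is still expected to continue. An emergency visit after early exit, to a hospital with no link to the referral clinic, has no assured path into the study data.

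The second is comparability. The event that ends the diary early is failure on the primary endpoint. Length of adverse-event observation is therefore tied to the efficacy result. If progesterone works as hypothesized, its arm is watched for longer, and a comparison of raw proportions mixes any true difference in tolerability with a difference in time observed.

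**Working it through.** **1. The plan's own figure.** Section 8 gives 20 per group for 68% v 25%, alpha 0.05, power 80%. With a two-sided test, pooled variance and no continuity correction, the mean rate is 0.465 and

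n = [1.96·√(2·0.465·0.535) + 0.842·√(0.68·0.32 + 0.25·0.75)]² / 0.43² = 19.9, so 20. It reproduces. These rates supply the arm-specific loss rates below: 32% and 75%.

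**2. Diary coverage after expulsion.** A woman who expels on day 3 and is seen on day 4 has about 1 day of post-expulsion diary. Her average course would run to day 12-19 (3 + 9 to 3 + 16), possibly to day 33 (3 + 30). If all visits are kept:
- shortest coverage: about 0 days (unscheduled visit on the day of expulsion);
- longest for an early exit: about 6 days (expulsion just after a day-3 visit, found on day 9);
- longest overall: about 10 days (expulsion just after a day-7 visit, found on day 17), which is 10/16 = 62% of a 16-day course and 10/30 = 33% of a 30-day course.

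If cardiac activity is found absent before the pregnancy has passed, the diary is collected before any expulsion.

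**3. Mean diary time by arm.** Let the full window be 16 days and every loss be found on day d. Mean days = P(continuing)·16 + P(loss)·d. The timing of losses is an assumption; the documents do not give it.

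| Losses found | Progesterone | Placebo | Gap (days) |
|---|---|---|---|
| all on day 4 | 0.68·16 + 0.32·4 = 12.2 | 0.25·16 + 0.75·4 = 7.0 | 5.2 |
| half day 4, half day 8 | 12.8 | 8.5 | 4.3 |
| a third each on days 4, 8, 16 | 13.9 | 11.0 | 2.9 |
| all on day 8 | 13.4 | 10.0 | 3.4 |
| all at scheduled exit | 16 | 16 | 0 |

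The gap is 0.43·(16 − d). A full window of 15 or 17 days moves the day-4 gap to 4.7 or 5.6 and the day-8 gap to 3.0 or 3.9. Counting from day 2 instead of day 1 takes one day off both arms and leaves the gap unchanged.

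**4. When the gap shrinks or reverses.** With 30% loss in both arms and the same timing, it is zero. Section 8 words the 25% as women who expel on mifepristone alone, but its 43-point effect needs 25% to be the continuing rate; these statements need reconciling. Taken literally (25% loss on placebo v 32% on progesterone), the day-4 means are 12.2 v 13.0, a gap of 0.8 days the other way.

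**5. Number of events.** Expected losses are 20·0.32 = 6.4 and 20·0.75 = 15, about 21 of 40. That is an upper limit on diaries cut short by loss, because a loss found at day 15-17 has a full diary. At Section 12's 1-5% rate of very heavy bleeding, expected events are 0.06-0.32 v 0.15-0.75.

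**The case against.** The strongest reply is that the diary is not the only safety source. Formal exit waits for a final outcome, referral-site records are copied, physicians are on call round the clock, heavy bleeding prompts an unscheduled visit, and an investigator reviews logged adverse events. Section 12 also says bleeding usually settles to menstrual level or less within hours of expulsion, so the most dangerous period may well fall inside the diary. Secondary comparisons are declared exploratory, and study drug stops at early exit, so a shorter side-effect window partly follows exposure.

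Much of this stands, and it rules out several stronger readings that a reader might infer:
- *That complications are under-recorded.* The documents show only that some may be. The 9-16 and 30 days describe expected bleeding or spotting, not complications.
- *That the arms have different windows by design.* They differ only if loss rates or timing differ, and only for losses found before day 15-17.
- *That the share of women with any adverse event would be visibly distorted.* The documents give no daily event rate, and Section 12 expects bleeding or spotting in every subject, so that share could be near 100% in both arms.
- *That incomplete expulsion and infection are named safety outcomes.* They appear as risks in Section 12, not among Section 6's examples.
- *That the referral clinics have no safety role.* Section 14 says "no staff at the PPMM Sacramento B Street Clinic or FPA Sacramento Clinic will be considered study personnel", but it also mentions co-investigators there and requires appropriate conduct.

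What the reply does not close: copied records give neither daily symptoms nor care the clinic never hears of; the final outcome has no stated definition or minimum duration; on-call cover depends on the woman making contact; and Section 14 limits procedures at those clinics to referral, specimens and records, with no adverse-event questioning assigned. Section 8 expects 36 of 40 women to come from them.

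**Conclusion.** The point holds in a limited form. It is a stated rule with a predictable effect on the safety comparison. The unassured information is self-reported bleeding and symptoms after early exit, and care obtained elsewhere, including emergency visits, which Section 6 lists as a safety outcome.

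The difference in mean diary time is conditional: 0 to 5.2 days with a 16-day window if the planning rates are right, depending on when losses are found. This assumes that 25% is the continuing rate on placebo, that loss timing is alike in the two arms, and that no one leaves early for other reasons.

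Few serious events are expected, so the arms cannot be separated on them in any case; but with 40 women, one missed event would change the safety result. The primary endpoint is not affected. The change is worth making because it is cheap and involves no change in treatment.

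**What to change.** - **At early exit**, still collect the drug and the completed diary: the diary holds the dosing record that the per-protocol set depends on. Give the woman a replacement bleeding and symptom sheet to keep until day 15-17.
- **Add one scripted safety call** by UCD research staff about 30 days after expulsion or surgical abortion, asking about emergency visits, transfusion, aspiration, infection and bleeding. The 30 days comes from Section 12's figure for bleeding after passing the pregnancy; for surgical cases it is an assumption.
- **In Section 10**, name review of referral-site records as a source of safety data.
- **In Section 8**, compare adverse events by arm over the common window from day 2 to day 15-17 for all randomized women. Because that window mixes on-drug and off-drug days after early exit, also report on-drug events with length of observation by arm.
- **In Section 5**, align the stated length of participation.

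Cost: a protocol amendment, consent wording and up to 40 calls by existing staff. Some sheets will not be returned, so the number missing should be reported by arm.

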A Randomized Trial of Mifepristone Antagonization with High-Dose Progesterone to Prevent Medical Abortion

NCT03774745

Protocol and SAP date: July 18, 2019 (version 10)

PROTOCOL TITLE: A Randomized Trial of Mifepristone Antagonization with High-Dose Progesterone to Prevent Medical Abortion

1) Protocol Title

Title: A Randomized Trial of Mifepristone Antagonization with High-Dose Progesterone to Prevent Medical Abortion

2) Objectives

Research questions:

1. Does high dose oral progesterone treatment increase the continuing pregnancy rate in women 44-63 days gestation exposed to mifepristone without misoprostol treatment?
2. If oral progesterone may be of benefit, do some characteristics of the pregnancy (e.g., gestational age) or patient (e.g. parity) potentially impact the outcome?
3. If oral progesterone may be of benefit, what sample size would be needed to validate such an outcome for various gestational age ranges in a prospective placebo-controlled randomized trial?
4. How long does it take to recruit women seeking surgical abortion to participate in a double-blind randomized trial evaluating oral progesterone for antagonization of mifepristone treatment for abortion?

Hypothesis: High-dose oral progesterone initiated 18-24 hours after mifepristone 200 mg in early pregnancy will result in more continuing pregnancies after 2 weeks of treatment than placebo.

3) Background

Medical abortion commonly refers to early pregnancy termination (usually before 10 weeks' gestation) performed without primary surgical intervention and resulting from the use of abortion-inducing medications (1). The use of medications to cause abortion has been around for almost 70 years but the modern era of medical abortion treatment evolved with the development of mifepristone (1), a progesterone-receptor blocker with an affinity for the receptor greater than progesterone itself (2).

Early research into modern medical abortion regimens took a leap forward with the discovery that adding a prostaglandin analogue within a few days after mifepristone significantly improved the efficacy of the treatment (3). In the late 1980s, France, China, Switzerland and the UK became the first countries to make medical abortion treatment clinically available, with regimens using mifepristone 600 mg followed 36-48 hours later by a prostaglandin analogue, restricted to use up to 49 days gestation.

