8) Data and/or Specimen Management and Confidentiality

Sample size:

- Delgado and colleagues estimate the oral progesterone regimen in this study has an efficacy of 68% (10) and that about 25% of women will expel the pregnancy after mifepristone 200 mg treatment alone, (10,12) implying an effect size of ~43%.
 - Sample size needed for Effect1=68%, Effect2=25%, Alpha=0.05, Beta=0.20: 20 per group.
 - Sample size needed for Effect1=70%, Effect2=25%, Alpha=0.05, Beta=0.20: 18 per group.
- We plan a convenience sample of 40 women (approximately 20 per group) which is enough to answer the primary question of efficacy proposed by Delgado and colleagues.
 - Should no obvious benefit be observed then a larger trial would not be indicated.
 - If some benefit is present, then a sample size could be estimated for a larger trial with considerations of sample size estimates for different gestational age ranges.
 - Importantly, if we cannot feasibly recruit from this population, then a larger study would also need to consider alternative mechanisms for enrollment.
- Recruitment: expect 36 subjects from PPMM and FPA (competitive enrollment) and 4 subjects from UCD.

Data Analysis Plan:

We will include all women randomized and perform intent-to-treat analysis with no apparent exclusions. In addition, a second analysis will be conducted with a per-protocol population, excluding women who do not report ingesting the study medication per protocol. Evaluations will include primary outcome (continuing pregnancy), expulsion rates, adverse effects, and treatment continuation rates.

At time of enrollment, we will collect baseline demographic data, including age, race, ethnicity, education level, and medical history (including obstetric and gynecologic history).

PROTOCOL TITLE: A Randomized Trial of Mifepristone Antagonization with High-Dose Progesterone to Prevent Medical Abortion

Fisher's Exact Testing will be used to compare outcomes and baseline characteristics in the two groups.

While not powered to detect a statistically significant difference among the two groups for secondary outcomes, exploratory analyses will be performed to identify possible trends and areas of interest for a subsequent larger trial. Chi square and Fisher's Exact Tests will be utilized to compare dichotomous variables as appropriate.

Data Management Plan:

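### The stated 80% power does not hold for the named Fisher's exact test: with 40 women, two-sided power is about 68–72% (about 79–80% if a one-sided test was meant)

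*Combined protocol and SAP*

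**What the plan says.** All the relevant text except the hypothesis is in Section 8.

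- **Sample size, first scenario:** "Sample size needed for Effect1=68%, Effect2=25%, Alpha=0.05, Beta=0.20: 20 per group".
- **Sample size, second scenario:** "Sample size needed for Effect1=70%, Effect2=25%, Alpha=0.05, Beta=0.20: 18 per group".
- **Adequacy claim:** "We plan a convenience sample of 40 women (approximately 20 per group) which is enough to answer the primary question of efficacy".
- **Rule for a larger trial:** "Should no obvious benefit be observed then a larger trial would not be indicated".
- **Test (Data Analysis Plan):** Fisher's "Exact Testing will be used to compare outcomes and baseline characteristics in the two groups". Chi-square appears only in the next paragraph, as an alternative for the exploratory secondary analyses.
- **Sidedness:** not stated. The hypothesis in Section 2 is directional: progesterone "will result in more continuing pregnancies after 2 weeks of treatment than placebo".

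The sample-size formula is not named. The plan says it is not powered for secondary outcomes, which implies that it is for the primary one.

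**The concern.** A sample size delivers its stated power only for the test it was derived for. The figures 20 and 18 are what uncorrected large-sample formulas give. Fisher's exact test holds its type I error well below the nominal level in samples this small, and it pays for that in power. If the primary comparison is a two-sided Fisher test, the type II error exceeds the stated 0.20.

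This matters because the claim that 40 women suffice for the primary question follows directly from the Beta=0.20 lines. A reader who believes the power is 80% will take a non-significant result as stronger evidence against the 43-point effect than it is.

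**Working it through.** **Inputs (Section 8).** Rates of 68% or 70% on progesterone and 25% on placebo, alpha 0.05, beta 0.20, about 20 per group. The rates are taken as given, with 25% read as the placebo continuing-pregnancy rate, as the plan's 43-point effect requires. Two-sided testing is assumed for the base case, and one-sided results are shown beside it.

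**Step 1: reproduce the plan's figures.**

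Two-sided arcsine formula: n = 2[(1.960 + 0.842)/h]², with h = 2·arcsin√p₁ − 2·arcsin√p₂.
- 68% v 25%: h = 0.892, n = 19.74, rounded up to **20**.
- 70% v 25%: h = 0.935, n = 17.95, rounded up to **18**.

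Two-sided pooled normal formula, 68% v 25%: p̄ = 0.465, and n = [1.960·√(2·0.465·0.535) + 0.842·√(0.68·0.32 + 0.25·0.75)]² / 0.43² = 19.90.

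Continuity correction, the usual approximation to Fisher's test: n′ = (n/4)[1 + √(1 + 4/(n·d))]², where d is the difference in rates. With n = 19.90 and d = 0.43, n′ = 24.33.

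| Formula | 68% v 25% | 70% v 25% |
|---|---|---|
| Two-sided arcsine | 19.74 | 17.95 |
| Two-sided pooled | 19.90 | 18.11 |
| Two-sided, continuity-corrected | 24.33 | 22.33 |
| One-sided pooled | 15.55 | 14.14 |
| One-sided, continuity-corrected | 19.93 | 18.32 |

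The plan's figures reproduce with an uncorrected two-sided formula. Of these, only the two-sided arcsine gives both 20 and 18 on rounding up.

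**Step 2: exact power of Fisher's test.** For each pair of counts (a, b), multiply the two binomial probabilities, and sum over all tables with Fisher p ≤ 0.05.

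| Progesterone/placebo | Two-sided, 68 v 25 | One-sided, 68 v 25 | Two-sided, 70 v 25 | One-sided, 70 v 25 |
|---|---|---|---|---|
| 20/20 | 0.685 | 0.786 | 0.731 | 0.823 |
| 19/21 | 0.703 | 0.789 | 0.749 | 0.828 |
| 21/19 | 0.718 | 0.803 | 0.759 | 0.837 |
| 18/22 | 0.713 | 0.800 | 0.757 | 0.837 |
| 22/18 | 0.721 | 0.804 | 0.764 | 0.840 |

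At the plan's 18 per group, 70% v 25%: 0.731 two-sided and 0.835 one-sided.

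**Step 3: group size needed for 80%, two-sided Fisher.**
- 68% v 25%: 23 per group gives 0.787 and 24 gives 0.819.
- 70% v 25%: 22 per group gives 0.795 and 23 gives 0.828.

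**Step 4: why power is lost.** At 20/20 the actual type I error of the two-sided Fisher test is at most 0.0253, about half the nominal 0.05. For example, 12/20 v 5/20 is a 35-point difference, yet p = 0.054.

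**Step 5: consequence if 68% v 25% is true, 20/20.**
- The chance of a non-significant two-sided result is 1 − 0.685 = 0.315.
- About 75% of those results would still show an observed difference of 25 points or more.
- The chance of an observed difference of 10 points or less is 1.9%, and of 20 points or less 7.8%.

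**The case against.** **Sidedness.** This is the strongest objection. The plan does not state it, the hypothesis is directional, and a one-sided Fisher test at 0.05 gives 78.6–80.4% for 40 women, so Beta=0.20 would be essentially met. Working back from the formulas does not settle the question: rounded to the nearest whole number, the one-sided continuity-corrected formula also gives 20 and 18. This stands. The shortfall depends on the two-sided reading, which is the usual default and the likelier one here, but is not established.

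**Chi-square.** The plan mentions it, and an uncorrected two-sided chi-square test has exact power of 0.786 at 20/20. That mention is confined to the exploratory secondary analyses, and the sentence on outcomes names Fisher alone, so this does not rescue the stated beta.

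**Convenience sample and first step.** The plan describes the sample and the study in these terms, and the rule for a larger trial is not tied to a significance test. It is therefore not shown that this rule would fail 3 times in 10; under the assumed effect, small observed differences would be rare. This limits the consequence. It does not remove the adequacy claim, which the plan makes outright.

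**Not a slip in calculation.** Correct: 20 and 18 are right for a large-sample test. The fault is that the sizing method does not match the analysis.

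**Conclusion.** The concern holds. Under a two-sided Fisher's exact test at 0.05 with 68% v 25%, 40 women give power of 68.5–72.1%, depending on the split. That is a type II error of about 0.28–0.32 against the stated 0.20, or 8 to 12 points less power than claimed. For 70% v 25%, power is 73.1% at 18 per group and 73.1–76.4% with 40 women.

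This rests on two assumptions: that the test is two-sided, and that the plan's rates are right. If one-sided 0.05 was meant, the stated power is met to within about 1.5 points at 68% v 25%, and what is missing is the statement of sidedness. Either way the text should be corrected. The design is not invalid, and the finding concerns how the trial's power is described and how a non-significant result will be read.

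**What to change.** In Section 8, with enrolment unchanged:

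1. In the sample-size bullets and the Data Analysis Plan, state that the primary comparison is a two-sided Fisher's exact test at 0.05. If one-sided 0.05 was intended, say that instead.
2. Replace the Beta=0.20 statements with power under that test. Two-sided: about 68–72% for 40 women at 68% v 25%, and about 73% for 18 per group at 70% v 25% (73–76% with 40 women). One-sided: about 79% at 20 per group and 84% at 18 per group.
3. Replace the claim that 40 women are enough with wording that gives this power. For the two-sided test, add that a non-significant result would occur about 3 times in 10 even if the 43-point effect were real.

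Optionally, before unblinding, Boschloo's exact test could be prespecified as the only primary test in place of Fisher. At 20 per group its power is about 78%, with a maximum type I error of 0.046. That is still just under 80%, and it is a choice, not a necessary correction.

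The cost is an edit to two bullets and two sentences; visits and data collection are unaffected. The drawback is a less favourable stated power, which may prompt the question why 80% is not reached.
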